APPENDIX III

genotypes modify the relationship between vitamin D levels and patient outcome. Cox proportional hazards models will be used to calculate multivariable-adjusted HRs and 95% CIs for DFS and OS by tertile of 25(OH)D for each SNP: those with the variant genotype and those with wild type. Tertiles will be used instead of quintiles for these analyses in order to maximize power. Tests for statistical interaction will be performed by entering into the model the cross-product term of 25(OH)D as a continuous variable with the genotype as a binary variable.

5.3 AGXT 154C>T polymorphism and neuropathy

The primary statistical objective for the pharmacogenetic companion of this study is to investigate the potential association between the AGXT 154C>T polymorphism and neuropathy in the Caucasian population.²²⁶ Specifically, it is hypothesized that the presence of the T allele is associated with higher incidence oxaliplatin-related peripheral neuropathy.

The primary statistical endpoint will be the realization of a grade 2 or higher neuropathy event. Let D denote the corresponding event and $\pi_i = P(D=1)$ denote the relative prevalence of the event in the population. The study will be powered assuming that the model is non-decreasing with respect to the T allele. In other words, it is assumed that $\pi_0 \leq \pi_1 \leq \pi_2$, where $\pi_0 = P(D=1|CC)$, $\pi_1 = P(D=1|CT)$ and $\pi_2 = P(D=1|TT)$. Assuming Hardy-Weinberg, the event probability is expressible as the mixture $\pi = (1-q)^2 \pi_0 + 2q(1-q) \pi_1 + q^2 \pi_2$.

The clinical study plans to contribute 2,500 patients to this intergroup study. It is assumed that 85% of these patients will provide consent and usable samples for this companion study. The analysis population will consist of those self-reported as Caucasian on the CRF form. The expected proportion for this population is at least 0.85. The companion study will be powered based on a sample size of 1806 ($=2500 \times 0.85 \times 0.85$).

The putative allelic relative frequency for the risk T allele is $q=0.3$. The power of the Cochran-Armitage test, at the two-sided 0.05 level, assuming a dominant model (DOM: $\pi_1 = \pi_2 = \pi_0 \times GRR$) and an additive model (ADD: $\pi_1 = \pi_0 \times GRR$, $\pi_2 = \pi_0 \times GRR \times GRR$) is illustrated in Table 1 for $GRR > 1$. Here GRR denotes the Genotype Relative Risk.

pi	GRR	Power	
		DOM	ADD
0.30	1.15	0.42	0.73
	1.20	0.62	0.92
	1.25	0.80	0.98
0.33	1.15	0.46	0.78
	1.20	0.69	0.95
	1.25	0.85	0.99

Table 1: Power illustration for the genotype test, at the two-sided 0.05 level, assuming a dominant or additive model.

It is noted that this is a hypothesis of association (gene by outcome) regardless of the number of cycles of oxaliplatin received. Any potential effect due to amount of therapy received will be examined using regression techniques.

Secondary SNPs of interest include potential predictive markers of outcome (OS or DFS) with respect to celecoxib (e.g., COX-2 and pathways) and germline variation in the vitamin D pathway.

The addition of other important clinical and demographic co-variables will be considered. Multivariable models, with molecular, clinical and demographic variables, will be constructed using conditional inference trees and random forests. All secondary and exploratory objectives will be tested at an unadjusted two-sided level of 0.05.

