The neurotoxic effects of oxaliplatin are not seen with exposure to the cytotoxic metabolite, DACH platinum, but rather with the oxalate metabolite. A promising biomarker for risk of oxaliplatin-associated peripheral neuropathy is AGXT, which encodes alanine-glyoxylate aminotransferase. Gamelin et al. proposed that key components of the oxalate synthesis pathway could be associated with platinum-drug neurotoxicity. In a study of 145 patients treated with oxaliplatin, a C to T change in AGXT nucleotide 154 was associated with risk of chronic neurotoxicity.²²⁶ Patients with a C/C genotype (~70% of Caucasians) had a significantly lower incidence of grade 2+ neurotoxicity (~5%) compared to the C/T and T/T patients (~30% of patients, expected incidence of grade 2+ neurotoxicity would be 30%). AGXT is a major enzyme of glyoxylate and oxalate metabolism and 154C>T has a partially reduced activity. These patients seem unable to cope with a brutal inflow of oxalate after oxaliplatin infusion, whose elimination becomes predominantly urinary. Its intracellular concentration increases and it interferes with sodium channels and generates acute neurotoxicity. Our primary hypothesis is

that patients with AGXT 154 C/T or T/T will have a significantly greater incidence of grade 2+ peripheral neuropathy, compared with 154 C/C patients.

Finally, in addition to specific hypothesis testing for the above candidate genes, this study will also provide the framework for hypothesis generation investigations of genotype and/or haplotype in additional candidate genes of putative importance to drug response of the agents being evaluated in this study.

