3.0 HYPOTHESES

- 3.1 Genetic variation in COX-2 and related pathway genes will influence the efficacy of adjuvant celecoxib on cancer recurrence.
- 3.2 Germline variation in vitamin D pathway genes (VDR, VDBP, CYP27B1, RXR, CYP24A1) will impact disease-free and overall survival in stage III colon cancer patients. Moreover, polymorphisms in these genes modify the effect of plasma 25(OH)D on patient outcome.
- 3.3 Patients with AGXT 154 C/T or T/T will have a significantly greater incidence of grade 2+ peripheral neuropathy, compared with 154 C/C patients.
- 3.4 Novel SNPs and/or copy number variations will be identified that are associated with the prevalence of oxaliplatin-related peripheral neuropathy as well as DFS and OS.
- 3.5 Genome-wide analyses will elucidate novel genes and pathways associated with risk of recurrence, survival, safety, and efficacy of treatments.
- 3.6 Genome-wide analyses will allow the ascertainment of the genetic basis of risk of sporadic CRC through participation in larger case-control studies of CRC predisposition.

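### AGXT power table (Appendix III, 5.3) uses a T-allele frequency of 0.3, which contradicts the roughly 70% C/C in section 2.3; at the frequency that 2.3 implies, additive-model power is up to 16 points lower

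*Combined protocol and SAP*

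**What the plan says.** Appendix III, section 5.3, covers the primary statistical objective of the pharmacogenetic companion: whether AGXT 154C>T is associated with grade 2 or higher neuropathy in self-reported Caucasian patients. On sample size it says "The companion study will be powered based on a sample size of 1806", from 2,500 × 0.85 × 0.85. It uses Hardy-Weinberg genotype proportions ("Assuming Hardy-Weinberg, the event probability is expressible as the mixture" of the three genotype-specific risks). On the allele frequency it says "The putative allelic relative frequency for the risk T allele is" 0.3, with no derivation. Table 1 then gives the power of a two-sided 0.05 Cochran-Armitage test under a dominant and an additive model.

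Appendix III, section 2.3, describes the study that motivates the analysis (reference 226, which 5.3 also cites): "Patients with a C/C genotype (~70% of Caucasians) had a significantly lower incidence of grade 2+ neurotoxicity (~5" per cent. The C/T and T/T patients together are put at about 30%, with an expected incidence of 30%. Hypothesis 3.3 of the same appendix compares carriers with non-carriers: "Patients with AGXT 154 C/T or T/T will have a significantly greater incidence of grade 2+ peripheral neuropathy, compared with 154 C/C patients".

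**The concern.** The two sections describe the same polymorphism in the same population and imply different genotype distributions. With q = 0.3 about half of the patients carry T. With 70% C/C fewer than a third do.

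The power of a trend test on allele count depends directly on the variance of that count, so an allele frequency that is too high makes the additive column too favourable. Table 1 is the only power statement for this objective, and the additive column is the only one with any cell above 0.85.

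**Working it through.** **Implied frequencies.** From 5.3, q = 0.3: C/C = 0.7² = 0.49, C/T = 2 × 0.3 × 0.7 = 0.42, T/T = 0.3² = 0.09, so carriers are 0.51. From 2.3, C/C = 0.70: q = 1 − √0.70 = 0.163, with C/T = 0.273 and T/T = 0.027. If the 70% is read loosely, 65% gives q = 0.194 and 75% gives q = 0.134.

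Dropping Hardy-Weinberg does not help. With 30% carriers, q = ½ P(C/T) + P(T/T), which lies between 0.15 and 0.30 and reaches 0.30 only if every carrier is T/T.

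**Power formula.** The inputs are N = 1,806, scores x = 0, 1, 2, genotype frequencies g, mean score x̄ = 2q, overall event rate π (0.30 or 0.33) and genotype relative risk GRR. The risks p solve Σ g·p = π, with p₁ = p₂ = GRR·p₀ (dominant) or p₁ = GRR·p₀ and p₂ = GRR²·p₀ (additive). Then

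- μ = N Σ g(x − x̄)p
- V₀ = N π(1 − π) · 2q(1 − q)
- V₁ = N Σ g(x − x̄)² p(1 − p)
- power = Φ[(μ − 1.96√V₀)/√V₁]

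**One cell in full** (additive, π = 0.30, GRR = 1.15).

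- q = 0.3: p = 0.275, 0.316, 0.363; μ = 32.66; √V₀ = 12.62; √V₁ = 12.78; power = Φ(0.620) = 0.732. Printed: 0.73.
- q = 0.163: p = 0.286, 0.329, 0.378; μ = 21.68; √V₀ = 10.18; √V₁ = 10.42; power = Φ(0.166) = 0.566.

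**All cells.**

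| π | GRR | Dominant: printed | q = 0.3 | q = 0.163 | Additive: printed | q = 0.3 | q = 0.163 |
|---|---|---|---|---|---|---|---|
| 0.30 | 1.15 | 0.42 | 0.420 | 0.417 | 0.73 | 0.732 | 0.566 |
| 0.30 | 1.20 | 0.62 | 0.629 | 0.629 | 0.92 | 0.922 | 0.797 |
| 0.30 | 1.25 | 0.80 | 0.799 | 0.802 | 0.98 | 0.986 | 0.931 |
| 0.33 | 1.15 | 0.46 | 0.470 | 0.466 | 0.78 | 0.790 | 0.624 |
| 0.33 | 1.20 | 0.69 | 0.690 | 0.689 | 0.95 | 0.952 | 0.850 |
| 0.33 | 1.25 | 0.85 | 0.851 | 0.854 | 0.99 | 0.994 | 0.959 |

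At q = 0.3 every printed cell is reproduced within 0.01, so both the method and the input behind the table are identified. Simulation with 40,000 trials per cell agrees with the formula within 0.01.

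**Range for 65% to 75% C/C, additive.** At π = 0.30 the power runs from 0.62/0.84/0.95 down to 0.50/0.74/0.89; at π = 0.33, from 0.68/0.89/0.98 down to 0.56/0.79/0.93.

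**Detectable additive GRR, q = 0.3 against q = 0.163.** For 80% power: 1.16 against 1.20 (π = 0.30) and 1.15 against 1.19 (π = 0.33). For 90% power: 1.19 against about 1.23 and 1.18 against 1.22.

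**Why the dominant column does not move.** Scores 0/1/2 misfit a dominant effect, and the misfit costs more when T/T is common. At π = 0.30 and GRR = 1.15, carrier scores 0/1/1 give 0.491 at q = 0.3 and 0.449 at q = 0.163, against 0.420 and 0.417 with scores 0/1/2. The smaller misfit at the lower q offsets the loss of carriers.

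**The case against.** The conflict between the two frequencies is hard to dispute. The objections concern the remedy and the weight.

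- **The event rate in 2.3 also differs from Table 1.** Its figures imply 0.70 × 0.05 + 0.30 × 0.30 = 0.125, not 0.30 or 0.33. At π = 0.125 and q = 0.163, power would be 0.18/0.27/0.38 (dominant) and 0.24/0.38/0.52 (additive), so changing q alone does not align the table with 2.3. This is true, but π labels the rows of the table as a planning value and may reasonably differ between treatment settings. Section 2.3 presents its genotype frequency as a property of Caucasians, the group that 5.3 analyses.
- **The dominant column is stable only at 70% C/C with allele-count scores.** At 75% C/C it is 0.39/0.60/0.77 (π = 0.30) and 0.44/0.66/0.83 (π = 0.33), 2 to 3 points below print. With carrier scores 0/1/1 the cell at π = 0.30 and GRR 1.15 falls by about 4 points, although those scores do not reproduce the table. This stands as a qualification.
- **Little depends on the table.** It is captioned an illustration, 5.3 calls the frequency putative, and 1,806 comes from accrual and consent fractions, not from a power target. For the contrast in 2.3, 5% against 30%, power stays near 1 at q = 0.163. This stands and limits the severity.

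**Conclusion.** The inconsistency is real, and its weight is minor. Table 1 was computed at q = 0.3, and section 2.3 implies 0.163 for the same population. If 2.3 is right, additive power is overstated by about 16 points at GRR 1.15, 10 to 12 at 1.20 and 3 to 5 at 1.25. The dominant column, which corresponds to the carrier hypothesis, is not materially affected.

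This rests on Hardy-Weinberg proportions, which 5.3 itself assumes, on allele-count scores, which the reproduction of the table supports, and on Table 1's own event rates. The documents do not show which frequency is correct. The 0.3 equals the carrier proportion in 2.3, so a carrier frequency may have been entered as an allele frequency, but nothing in the text establishes that.

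**What to change.** Reconcile q in 5.3 with the genotype frequencies in 2.3, in one of two ways:

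- give the source for q = 0.3 and correct the C/C and carrier percentages in 2.3; or
- set q = 0.163, restate the additive column as 0.57/0.80/0.93 (π = 0.30) and 0.62/0.85/0.96 (π = 0.33), and leave the dominant column as it is.

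A sentence on the basis for π would also help, since 2.3 suggests a lower overall rate.

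The second option costs one corrected input, six restated cells and less favourable additive figures. Neither option needs more patients or changes the test, the significance level or any trial endpoint.

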8.6 Neurotoxicity

Toxicity Scale for the Sensory Neuropathies Associated with Oxaliplatin (using the Oxaliplatin Specific Neurotoxicity Scale)

	Symptoms
Grade 1	Paresthesias/dysesthesias* of short duration that resolve and do not interfere with function.
Grade 2	Paresthesias/dysesthesias* interfering with function, but not with activities of daily living (ADL)
Grade 3	Paresthesias/dysesthesias* with pain or with functional impairment that also interfere with ADL.
Grade 4	Persistent paresthesias/dysesthesias* that are disabling or life threatening.
	* May be cold-induced

- 8.6.1 For grade 2 neurotoxicity persisting between treatments:** Continue FOLFOX with one dose level reduction of oxaliplatin for all subsequent cycles and the previous dose level of 5-FU. Continue celecoxib/placebo.
- 8.6.2 For grade 3 neurotoxicity resolving to \leq grade 2 between treatments:** Continue FOLFOX with one dose level reduction of oxaliplatin for all subsequent cycles and the previous dose level of 5-FU. Continue celecoxib/placebo.
- 8.6.3 For grade 3 neurotoxicity persisting between treatments:** Discontinue oxaliplatin. Continue 5-FU/leucovorin and celecoxib/placebo.
- 8.6.4 For grade 4 neurotoxicity:** Discontinue oxaliplatin. Continue 5-FU/leucovorin and celecoxib/placebo.
- 8.6.5 For pharyngolaryngeal dysesthesia:** Increase the duration of oxaliplatin infusion to 6 hours for all subsequent cycles. See also [Section 8.8.1](#).

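### The primary AGXT–neuropathy test is valid, but it leaves out randomised FOLFOX duration; stratifying by it is a free gain in power of modest, uncertain size

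*Combined protocol and SAP*

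**What the plan says.** Appendix III, Section 5.3 makes the AGXT question the primary statistical objective of the pharmacogenetic companion. On the endpoint: "The primary statistical endpoint will be the realization of a grade 2 or higher neuropathy event". On the test: "The power of the Cochran-Armitage test, at the two-sided 0.05 level, assuming a dominant model", and likewise under an additive model. The sample size is 1806, the risk allele frequency 0.3 and the overall event rate 0.30 or 0.33. The results are in Table 1, captioned "Power illustration for the genotype test, at the two-sided 0.05 level, assuming a dominant or additive model". No stratification is mentioned.

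Two sentences deal with exposure. The first is "It is noted that this is a hypothesis of association (gene by outcome) regardless of the number of cycles of oxaliplatin received". The second is "Any potential effect due to amount of therapy received will be examined using regression techniques"; it gives no model, no covariate form and no inferential status. The end of Section 5.3 leaves other clinical and demographic covariates for consideration. Randomised duration is not named in any of these places.

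In the main protocol, Section 7.0 sets 6 or 12 FOLFOX cycles by randomisation. Objective 2.2.6 compares toxicity, cumulative neuropathy in particular, between those arms. Sections 1.5 and 1.9 give neuropathy as a main reason for testing the shorter course.

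Under Section 8.6, oxaliplatin is reduced for persistent grade 2 neurotoxicity and for grade 3 that resolves to grade 2 or lower. For persistent grade 3, and for grade 4, the text is "Discontinue oxaliplatin. Continue 5-FU/leucovorin and celecoxib/placebo".

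**The concern.** Randomised duration is known for every patient before treatment, is independent of germline genotype, and is expected by the trial's own rationale to be related to the endpoint. Stratifying a binary-outcome test on such a factor removes between-arm variation from the denominator and leaves the genotype signal intact. Leaving it out gives up power, and most of the dominant-model entries in Table 1 are below 0.80.

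The one exposure variable the section does name is amount of therapy received. Section 8.6 makes that partly a result of neuropathy. Appendix III, Section 2.3 also says that patients on oxaliplatin stop more often for neuropathy than for progression. A regression that conditions on amount received can therefore absorb part of a genotype effect on neuropathy, whereas one that uses the randomised arm cannot.

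**Working it through.** **Inputs.** From Section 5.3: n = 1806 (2500 × 0.85 × 0.85 = 1806.25), q = 0.3, two-sided 0.05, overall rate π = 0.30, GRR 1.15 to 1.25. Hardy-Weinberg genotype frequencies f are 0.49, 0.42 and 0.09, with scores x = 0, 1, 2. Assumed, because the documents do not give them: 1:1 allocation to duration, the neuropathy rate in each arm, and the same GRR in both arms.

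**Step 1: reproduce Table 1.** Power ≈ Φ[(√n·C − 1.96·√V0)/√V1], where C = Σf·p·(x − x̄), V0 = π(1 − π)·Var(x) and V1 = Σf·p(1 − p)(x − x̄)². Here x̄ = 0.6 and Var(x) = 0.42. For the dominant model at GRR 1.20:

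- CC risk = 0.30/(0.49 + 0.51 × 1.20) = 0.2722; carrier risk = 0.3267
- C = 0.294 × (0.3267 − 0.2722) = 0.0160; √n·C = 0.680
- V0 = 0.21 × 0.42 = 0.0882, root 0.2970; V1 = 0.0885, root 0.2975
- Power = Φ[(0.680 − 0.582)/0.2975] = Φ(0.330) = 0.629, against 0.62 printed

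The other dominant entries at π = 0.30 come out at 0.420 and 0.799 (printed 0.42 and 0.80). The additive ones are 0.732, 0.922 and 0.986 (printed 0.73, 0.92 and 0.98). All 12 entries reproduce within 0.02.

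**Step 2: stratify by randomised duration.** With a common GRR, C is unchanged. V0 becomes 0.42 times the mean of π(1 − π) over the two arms. For an arm difference d, the ratio of new to old V0 is 1 − d²/(4 × 0.21), which depends on neither q nor GRR. At 15/45 the mean is (0.1275 + 0.2475)/2 = 0.1875, the ratio is 0.1875/0.21 = 0.893, and the gain is worth 1/0.893 = 1.12 times the patients. Power is Φ[(0.680 − 1.96 × 0.2806)/0.2807] = Φ(0.464) = 0.679.

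| Assumed rates, 6 / 12 cycles | Variance ratio | Gain in effective n | Dominant, GRR 1.20 | Dominant, GRR 1.25 | Additive, GRR 1.20 |
|---|---|---|---|---|---|
| 0.30 / 0.30 | 1.000 | 0% | 0.629 | 0.799 | 0.922 |
| 0.25 / 0.35 | 0.988 | 1% | 0.634 | 0.803 | 0.925 |
| 0.20 / 0.40 | 0.952 | 5% | 0.651 | 0.818 | 0.934 |
| 0.15 / 0.45 | 0.893 | 12% | 0.679 | 0.842 | 0.949 |
| 0.10 / 0.50 | 0.810 | 23% | 0.721 | 0.876 | 0.966 |

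The first row equals the unstratified test. Results at π = 0.33 are similar.

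**Step 3: the separate regression.** A logistic simulation (500 replicates, n = 1806, additive GRR 1.20, arms 0.15/0.45) assumed that 60% of neuropathy cases stop early and that 10% of patients stop at random for other reasons.

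| Covariates besides genotype | Genotype log OR | Power |
|---|---|---|
| None | 0.261 | 0.916 |
| Randomised arm | 0.296 | 0.944 |
| Cycles received | 0.264 | 0.918 |
| Arm and cycles received | 0.285 | 0.890 |

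The cleanest comparison is arm against arm plus cycles: the log OR falls from 0.296 to 0.285 and power from 0.944 to 0.890. With 30% stopping early the same comparison gives 0.301 against 0.300, and 0.938 against 0.930. The Monte Carlo standard error of a power near 0.92 is √(0.92 × 0.08/500) = 0.012. With no genotype effect, rejection rates ran from 0.022 to 0.062 over all models and stopping assumptions, against a standard error of about 0.010, so there was no sign of inflation.

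**The case against.** The strongest reply is that nothing in the primary analysis is wrong. A marginal gene–outcome association is a legitimate target, and the plan states it on purpose. Genotype is independent of the randomised arm, so omitting the arm causes no confounding and no type I error problem, and Table 1 is right for the test as specified. All of that stands. Stratifying by assigned duration still answers the same question, since it uses the randomised arm and not the cycles received.

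The gain may also be small. The documents give no arm rates, and objective 2.2.6 states no expected size. The endpoint is any grade 2 or higher event, not persistent neuropathy. Section 9.1 reports acute sensory neuropathy in about 56% of patients, arising soon after a dose, and both arms share the first six cycles. Under the additive model the power at GRR 1.20 is already 0.92. This limits the size claimed but gives no reason to leave the arm out.

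A reader might infer that the primary test adjusts for therapy received and so conditions on a consequence of neuropathy. Section 5.3 says the opposite: the test is run regardless of cycles received. A reader might also infer that the plan commits to a biased adjusted estimate. It does not specify such a model or say that the conclusion rests on one. Stopping oxaliplatin is confined to persistent grade 3 and to grade 4, and persistent grade 2 leads only to a dose reduction, so many endpoint events need not change the number of cycles. The 60% early-stopping figure used above is an assumption.

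The open wording on other covariates does not exclude adjusting for duration, but it does not commit to it either.

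**Conclusion.** The point holds as a matter of efficiency. The primary AGXT test is valid, and stratifying it by randomised duration would add power without changing its endpoint, population or significance level. At π = 0.30 and GRR 1.20 the gain is about 0.5 to 9 percentage points under the dominant model, and 0.3 to 4.4 under the additive model, for assumed arm differences of 0.10 to 0.40. It is zero if the arms do not differ. These figures rest on assumed arm rates, 1:1 allocation and a common GRR.

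The caution about amount of therapy received applies only to the secondary regression. There the expected effect is some attenuation of the genotype effect and some loss of power. Its size depends on how often neuropathy shortens treatment, which the documents do not quantify.

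**What to change.** In Appendix III, Section 5.3:

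- Name as the primary test the Cochran-Armitage (Mantel-type) trend test stratified by randomised FOLFOX duration (6 versus 12), with score and variance summed over the two strata. Keep the endpoint, population and two-sided 0.05 level. The unstratified result can be reported beside it.
- State that the secondary regression includes randomised duration.
- Keep amount of therapy received as an exploratory question if wanted. Give the model and covariate form, and note that amount received is partly a consequence of neuropathy, so the genotype coefficient in that model may be attenuated.

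Table 1 can stay, as the power of the unstratified test. The cost is wording only, since the arm is known for every patient. The change should be made before genotype and outcome data are analysed together.
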